APPENDIX A: ABBREVIATIONS AND ACRONYMS

CEC	Clinical Events Committee
MAB	Medical Advisory Board
AE	Adverse Events
DSMB	Data Safety and Monitoring Board
HF	Heart Failure
ECG	Electrocardiogram
BTT	Bridge to transplant
VAD	Ventricular Assist Device
TTE	Transthoracic echocardiography
FDA	Food and Drug Administration
TEE	Transesophageal echocardiography
CRT	Cardiac Resynchronization Therapy
NYHA	New York Heart Association
QOL	Quality of Life
LVAD	Left Ventricular Assist Device
DT	Destination Therapy
IAB	Intra-Aortic Balloon
IDE	Investigational Device Exemption
ICP	Implantable Counterpulsation Pump
PIL	Percutaneous Interface Lead
IR	Infra–red
CPX	Cardiopulmonary Exercise Testing
IRB	Investigational Review Board
MLWHF	Minnesota Living With Heart Failure
KCCQ	Kansas City Cardiac Quality of Life Questionnaire
CXR	Chest X-ray
ECHO	Echocardiogram
eCRF	Electronic Case Report Form Template
ICU	Intensive Care Unit
IV	Intra–venous
PRBC	Packed Red Blood Cells
MCS	Mechanical Circulatory Support Device
GFR	Glomerular Filtration Rate
TAPSE	Tricuspid Annular Systolic Excursion
CTS	Cardiothoracic Surgeon
HFC	Heart Failure Cardiologist

APPENDIX B: SUMMARY OF PREVIOUS STUDIES

Experience to date by Sunshine Heart Inc. provides evidence of safety and performance. These include:

INTRA-OPERATIVE CLINICAL FEASIBILITY STUDY

The aim of this study was to determine the safety and performance of a new method of non-blood contacting counterpulsation utilizing an inflatable Cuff (C-Pulse) around the ascending aorta.

In 6 patients undergoing first time off pump coronary bypass surgery via sternotomy, the C-Pulse was secured around the ascending aorta and attached to a standard counterpulsation console. At baseline, and with 1:2 and 1:1 augmentation, hemodynamic and echocardiographic parameters of ventricular function and coronary flow were measured. High intensity transient signals (HITS) were measured using transcutaneous Doppler over the right common carotid artery.

No complications occurred.

With C-Pulse there was no significant change in heart rate and blood pressure, and no increase in HITS. There was a 67% increase in diastolic coronary blood flow (mean left main diastolic velocity time integral 15.3 cm unassisted vs. 25.1 cm assisted, $p < 0.05$). Measurements with transesophageal echocardiography, at baseline and with 1:1 counterpulsation, demonstrated a 6% reduction in end diastolic area ($p = \text{NS}$), 16% reduction in end systolic area ($p < 0.01$), 31% reduction in LV wall stress ($p < 0.05$), and a 13 % improvement in fractional area change ($p < 0.005$). It was concluded that C-Pulse System counterpulsation augments coronary flow and reduces left ventricular afterload.²⁴

LONG-TERM EXTRA-AORTIC BALLOON COUNTERPULSATION IN SHEEP

This study was undertaken to examine the effect of chronic counterpulsation with C-Pulse on the integrity of the ascending aorta in sheep at 5 and 10 months.

A pre-shaped cuff, consisting of a polyurethane balloon and polyester wrap, was implanted around the ascending aorta via a left mini-thoracotomy in 11 adult sheep. An endocardial ECG sensing lead was implanted via the right external jugular vein. The balloon's gas line and the sensing lead were brought out percutaneously over the back and connected to a Datascope 90 IABP console.

²⁴ Legget 2005

Sheep were counterpulsated for approximately five and ten months. Prior to post-mortem, intra-aortic ultrasound examination was completed to examine balloon function. Following euthanasia, an autopsy was conducted in all sheep; particular attention was paid to the heart, brain and kidneys. Detailed histology was completed on the heart and great vessels with the attached device, from each sheep.

Intra-aortic ultrasound showed each cuff to be inflating and deflating in a normal pattern following 5 and 10 months operation. Sheep were terminated at five months (6) and 10 months (5).

One sheep was euthanized at 5 months because it became ill over several days; at autopsy it was found to have a bacterial infection involving the cuff and the aorta resulting in a contained aortic rupture. In two other sheep (at 5 and 10 months, respectively) non-disruptive aortitis was noted at post-mortem and this was confirmed by microscopic pathology.

Hence the thoracic aorta was assessed microscopically in 8 sheep; 4 at 5 months and 4 at 10 months. Histology of the aortic wall at the root and arch appeared normal. Sections through the mid-ascending aortas revealed the peri-aortic implants were well incorporated by the adventitial peri-aortic tissues and that there was no disruption to the endothelial surfaces. Histology demonstrated that for each of the 8 sheep the intima and inner half of the media, measuring 0.6–0.9 mm thick, appeared normal. Findings in the outer one third to one half of the aortic wall included muscular atrophy, thin-walled blood vessels, petechial hemorrhages, small focal strips of coagulative necrosis (0.1–0.3 mm thick) and viable reparative tissue responses. Those at 10 months displayed a recognizable reparative microvascular (arterial and venular) pattern with less necrosis than at 5 months. The changes were circumferential. While the cuffed aortic wall was thinner than the normal wall, there was no evidence of progressive damage to the inner media and intima when comparing results from sheep at 5 months to those at 10 months.

- Demonstrate feasibility of device/procedure
 - Assess learning curve
 - Refine technology and implant technique
- Provide reasonable assurance of safety
 - Learn how to mitigate risk
- Explore preliminary efficacy signals
- Support design of subsequent pivotal trial

The study was not powered to detect statistical significance. As such, clinical judgment and assessment of the totality of the data are required to evaluate device safety and potential efficacy from data collected during this study. This clinical judgment was provided by the independent DSMB.

²⁵ [Hayward 2010]

The DSMB reviewed the entire dataset prior to submission to FDA in November 2011. The DSMB recommendations were:

- Implement dressing change procedures and processes to reduce the infection rate.
- Ask patients if they are on a transplant list prior to enrollment to differentiate between patients that had plans for transplant vs. patients without plans for transplant that received one.
- Provide the feasibility data to the FDA as soon as possible in order to start the pivotal trial and enroll patients under a controlled study.

The aforementioned objectives were met in several ways. The technology was refined, such that a minimally invasive approach to implantation was developed and successfully implemented during the trial. Other technology refinements (e.g., enhancements to Driver hardware and software) were also made. The feasibility of device explantation for “weaning” to native function, device explantation for transplant and device explantation for placement of left ventricular assist devices were demonstrated successfully in the trial. Subjects were supported on the device for a total of 5,439 days, with a mean of 272 days, median of 230 days and a range of 60 to 644 days.

Risk mitigation strategies were developed, including a revised infection control guideline, new PIL stabilization accessory and lead management strategy to be implemented in the pivotal trial. The primary safety endpoint demonstrated that the device related events were substantially lower in some categories (e.g. neurological dysfunction, bleeding) compared to other heart assist devices. The exit site infections were the primary SAE reported. The exit site infections were treated and managed in an outpatient setting. Despite the infections, the subjects continued therapy to the next stage of their heart failure cascade whether transplant, LVAD or recovery.

The primary efficacy endpoint of NYHA demonstrated 12 out of 15 subjects had at least a one Class improvement. In addition, the primary efficacy endpoint of MLWHF demonstrated 13 out of 15 subjects had at least a seven point decrease (improvement) in MLWHF. The 6MHW demonstrated trends toward efficacy. The Peak VO₂ testing did not show a trend toward a positive response but did not demonstrate a negative response. Other observations support the potential efficacy of the C-Pulse[®] System. For example, inotropes were weaned in all subjects whom had inotropes prior to implant. Diuretic doses were able to be decreased in some subjects. The LVEF, Septal E/E, mitral regurgitation, wedge pressure, LVEDD, LVEDV and CI tended to demonstrate improvement supporting the benefit of LV unloading with the C-Pulse. The initial North American experience demonstrated that the C-Pulse System met the intended use for the device with trends toward efficacy and reasonable assurance of safety with a minimal adverse event profile. Subjects enrolled and implanted with the C-Pulse System were able to be discharged, lived through the post-op period experiencing an improved quality of live than prior to implant. The therapy is treating patients with severe-to-moderate heart failure at a stage in the cascade of the failure in a way that benefits subjects at home providing an increased quality of life compared to alternative therapies. One distinct advantage of the C-Pulse System is the absence of a blood contacting surface, limiting the risk of thrombosis/thromboembolism or the risk of bleeding seen with devices requiring anticoagulant therapies. The preliminary risk/benefit profile of the C-Pulse, supported by this feasibility study, made it a potentially attractive option for the intended patient population (ACC/AHA Stage C, NYHA Class III to ambulatory Class IV patients) and warranted a pivotal trial.

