Patients will be enrolled into the trial upon providing informed consent. Each subject will be randomized after meeting the Eligibility Criteria and completion of baseline testing. Due to time required for baseline testing and scheduling of implant, sites will manage these items within the 30 day window as suited for the individual institution and patient. Procedures related directly to the study must not be performed prior to informed consent. Data collection will be noted prior to implantation of the device and at six months following implant, then long term at 12 and 18 months followed by annually post-implant for five years. Serious adverse events (SAE) will be collected throughout the study until study closure and will be adjudicated by an independent Clinical Event Committee (CEC).

Progress reports of the clinical outcomes will be reviewed by the DSMB after randomization of forty (40) patients and at least twice annually based on study progress. A progress report will be sent to FDA for review as specified in the Statistical Methods and Data Analysis section.

The total duration of the study including the enrollment and 12 month follow-up is expected to be approximately 36-42 months.

OBJECTIVES

Primary Objectives

The primary objectives of the study are to demonstrate the safety and efficacy of the C-Pulse therapy as compared to OMT. Refer to the section on Statistical Methods and Data Analysis for a detailed discussion of the definitions and methodology.

1. Primary Efficacy Objective:

To demonstrate the superiority of the C-Pulse therapy in increasing survival free from worsening heart failure resulting in hospitalization, LVAD implantation, cardiac transplantation or death as compared to OMT.

2. Primary Safety Objective:

To demonstrate the safety of the C-Pulse System by evaluating freedom from serious adverse events that are adjudicated as definitely related to device, therapy or procedure and resulting in either surgical intervention or death.

Secondary Objectives

The secondary objectives are as follows:

1. To demonstrate the superiority of C-Pulse therapy as compared to the OMT Control in improvement in 6 Minute Hall Walk score at 12 months post-randomization.
2. To demonstrate the superiority of C-Pulse therapy as compared to the OMT Control in improvement in 6 Minute Hall Walk score at 18 months post-randomization.

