In the event the subject becomes lost to follow-up, the investigational site should make two documented attempts to contact the subject. A Study Exit record must be completed and the subject will no longer be followed in the clinical study.

Data Collection Overview

A review of patient files is required to determine preliminary eligibility according to patient inclusion and exclusion criteria. Baseline data including functional tests must be collected no more than **30** days prior to randomization. Baseline imaging such as echo and CT scans must be collected no more than 90 days prior to randomization. See the data collection table for details.

Follow-up data will be collected at the time of implant, hospital discharge, at planned follow-ups (6 week, 3, 6, 12, 18-month and annually from the implant date thereafter up to 5 years). All serious adverse events will be collected throughout the study until closure.

All study subjects will follow the prescribed follow-up scheduled despite randomization. Day 0 for the treatment group will be the day of implant. Day 0 for the Control Group will be the day of randomization. Each group will continue with optimal medical therapy for the duration of the study, including all standard of care medications and treatments including transplant, VAD, etc. If the subjects are transplanted or placed on another device they will be censored from the primary endpoint analysis and study exited. Subjects implanted with the C-Pulse will be followed until device removal. If the PIL is explanted and not replaced, the subject will be followed for safety until removal of the entire system.

Data will be collected via electronic data capture (EDC) screens referred to as e-case report forms (eCRFs). Echocardiogram tapes and digital storage media must be documented in the patient medical record for source documentation.

Table 1, below outlines the data collection with the appropriate follow-up time windows.

Table 1. Follow-up Windows

Evaluation	Time Window
Pre-Implant Evaluation	No more than 30 days prior to implant
Randomization	Post Baseline Testing and Pre-Implant
Implant	Day 0 (Treatment Group) – Implant Day 0 (Control Group) – Randomization
Pre-Discharge	Within 36 hours prior to discharge
6 – week follow-up	Days 42 ± 7 Post-Implant
3 – month follow-up	Days 90 ± 14 Post-Implant
6 – month follow-up	Days 180 ± 30 Post-Implant
12 – month follow-up	Day 365 ± 30 Post-Implant
18 – month follow-up	Day 540 ± 30 Post-Implant

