Report all associated adverse events. Update the device tracking records with all products. If the device is not returned to Sunshine Heart Inc., justification must be provided in the log.

Subject Withdrawal and Study Exit

A Study Exit record shall be completed if subject is unable to or refuses to continue participation in the study. Notify the Sunshine Heart clinical support team as soon as possible upon learning of a subject withdrawal/study exit.

If the subject fails to comply with follow-up visits, the study center must make repeated attempts to contact the subject. Each attempt to contact the subject must be documented in the subject's records and in the database.

If the subject officially withdraws from the study, the investigator will document the reason for withdrawal and indicate any relationship of the withdrawal to the study or the device on the eCRF.

If a subject withdraws from the study at any time, there will be no penalty or loss of future medical care.

STATISTICAL METHODS AND DATA ANALYSIS

Analysis Population

All randomized subjects will be included in the evaluation of the primary efficacy objective. Subjects will not be allowed to cross-over. All subjects implanted with the C-Pulse System will be included in the evaluation of the primary safety objective. In the event a randomized subject does not receive the implant or does not receive the randomized therapy, the subject will be analyzed according to the randomized assignment for the primary analyses. Additional supporting analyses of the primary efficacy endpoint will be conducted (as treated and per-protocol) which exclude subjects who do not receive the randomized treatment or those with major protocol deviations. The defined analysis cohorts are:

- Intent to treat: All randomized subject irrespective of treatment actually received (primary efficacy analysis)
- As treated: All randomized subjects receiving treatment as randomized
- Per protocol: All randomized subjects without major protocol deviations

Primary Efficacy Endpoint

The primary efficacy endpoint is defined as freedom from worsening heart failure related hospitalization, LVAD implant, heart transplant, and death.

The primary efficacy endpoint includes all occurrences of worsening heart failure events and will be analyzed utilizing a multiple failure time analysis.

Hypotheses

H_0 : HR=1,

H_A : HR \neq 1,

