The poolability of the primary efficacy endpoint across clinical sites will be assessed using a covariate adjusted proportional hazards regression model including an interaction term for clinical site and treatment group. In the event statistical evidence of a difference in treatment effect by site is found, an analysis utilizing a random effects model with a random effect for site will be conducted.

Type I Error Control for Secondary Objectives

The secondary efficacy objectives will be tested in a hierarchical fashion in the order listed only in the event the primary efficacy objective is met, thereby preserving an overall Type I error rate of 5%.

Handling of Missing Data

For the primary efficacy analysis, subjects lost to follow-up or explanted will be censored at the date of the last assessment.

Additional analyses of the follow-up assessments of KCCQ, six minute walk and LVEF will be conducted to assess the impact of missing data at month 12. The Wilcoxon Sign-Rank test with the worst rank imputed for data missing due to death, LVAD transplant, heart transplant or explant (in order of time to outcome) will be used to assess treatment differences in the continuous parameters while including subjects who withdrew from randomized treatment prior to the 12 month assessment. Multiple imputation analyses will be conducted to assess the robustness of the study results against data missing due to losses to follow-up and study non-compliance or un-interpretable test results.

Impact of Covariates on the Potential Treatment Differences

Additional exploratory statistical analyses of the primary and secondary study results will be conducted to assess for impact of selected baseline and follow-up parameters on the observed treatment differences. This will involve the stratification of results by categorical parameters and covariate adjusted regression analyses for the assessment of interaction with randomization assignment. Of particular interest will be an assessment for any treatment differences in the efficacy or safety parameters by gender. Other baseline covariates of interest will include classification based on race/ethnicity, age at implant, INTERMACS profile, NYHA, etiology (ischemic/non-ischemic), CRT/ICD therapy, angina, arrhythmia, hyperlipidemia and diabetes and the continuous covariates of baseline six-minute walk, KCCQ and MLWHF.

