APPENDIX G: HEART FAILURE ASSESSMENTS

NYHA Classification

In 1928, the New York Heart Association published a classification of patients with cardiac disease based on clinical severity and prognosis. This classification has been updated in seven subsequent editions of Nomenclature and Criteria for Diagnosis of Diseases of the Heart and Great Vessels (Little, Brown & Co.). The ninth edition, revised by the Criteria Committee of the American Heart Association, New York City Affiliate, was released March 4, 1994. These classifications are summarized below.

Class I. Patients with cardiac disease but without resulting limitation of physical activity. Ordinary physical activity does not cause undue fatigue, palpitation, dyspnea, or angina.

Class II. Patients with cardiac disease resulting in slight limitation of physical activity. They are comfortable at rest. Ordinary physical activity results in fatigue, palpitation, dyspnea, or angina.

Class III. Patients with cardiac disease resulting in marked limitation of physical activity. They are comfortable at rest. Less than ordinary activity causes fatigue, palpitation, dyspnea, or angina.

Class IV. Patients with cardiac disease resulting in inability to carry on any physical activity without discomfort. Symptoms of heart failure or the anginal syndrome may be present even at rest. If any physical activity is undertaken, discomfort is increased.

ACC/AHA Stages of Heart Failure

In 2001, the ACC/AHA published an update subdividing clinical heart failure into four ‘stages’. The stages are listed below:

Stage A. Patients at high risk for developing clinical HF (i.e. those with hypertension, diabetes, dyslipidaemia, and so on), but without detectable structural heart disease.

Stage B. Patients with detectable structural heart disease (i.e. LVH, LV Dysfunction), but no clinical signs or symptoms of HF.

Stage C. Patients with current or past clinical HF.

Stage D. Patients with end-stage refractory HF, who are candidates for extraordinary forms of therapy or for compassionate end-of-life care.

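### Heart transplant is a primary efficacy component, but the protocol neither specifies recording or using transplant-list status, as the feasibility DSMB advised, nor gives one consistent rule for transplant in the primary analysis.

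*Combined protocol and SAP*

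**What the plan says.** **Endpoint.** Under Primary Efficacy Endpoint: "The primary efficacy endpoint is defined as freedom from worsening heart failure related hospitalization, LVAD implant, heart transplant, and death". No exception is made for a transplant already planned at entry. The Primary Efficacy Objective is worded causally: "survival free from worsening heart failure resulting in hospitalization, LVAD implantation, cardiac transplantation or death as compared to OMT".

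**Censoring.** The Data Collection Overview says the opposite of the endpoint definition: "If the subjects are transplanted or placed on another device they will be censored from the primary endpoint analysis and study exited". The same paragraph keeps transplant available in both arms, with optimal medical therapy continued "including all standard of care medications and treatments including transplant, VAD, etc".

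**Feasibility advice.** Among the DSMB recommendations in Appendix B (US IDE Feasibility Study) is "Ask patients if they are on a transplant list prior to enrollment". The stated aim is to distinguish patients who already had transplant plans from those who had none and received one.

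**Where list status could appear but does not.**
- Inclusion and Exclusion Criteria: the only criterion naming cardiac transplantation excludes a prior one.
- Table 2: a general Medical History line, with no list-status item.
- Subject Eligibility Committee: four named items, none on listing.
- Impact of Covariates: "Other baseline covariates of interest will include classification based on race/ethnicity, age at implant, INTERMACS profile, NYHA", followed by etiology, CRT/ICD therapy and others, without listing.
- Design: randomization is stratified by center only.

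**Related text.** Exclusion 4 bars Stage D, which Appendix G describes as "Patients with end-stage refractory HF, who are candidates for extraordinary forms of therapy" or for compassionate end-of-life care. No passage says how being listed relates to that stage.

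**The concern.** For a subject already listed at randomization, the date of transplant depends on donor availability as well as on worsening heart failure. The objective speaks of worsening heart failure that leads to transplantation. The endpoint definition counts transplant without qualification. The two agree only if someone can establish why a given transplant took place, and list status at entry is the most direct evidence for that. The sponsor's own DSMB had asked for it.

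What is at stake depends on which passage governs:
- **Transplant counts as an event.** Planned transplants are events on which the device may have little or no effect, so they pull the hazard ratio toward 1.
- **Transplant is censored.** Dilution by this route disappears. Follow-up then ends at a time that may be related to prognosis, and list status is needed to judge whether that censoring is informative.

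In both cases the status is most credible when recorded before randomization. Status sought after a transplant, with the arm known, can be questioned.

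**Working it through.** **1. The plan's own figures (Primary Efficacy Endpoint Sample Size).** Inputs: two-sided alpha 0.05, power 0.80, control 6-month event-free proportion 0.72, HR 0.70, accrual 2.5 years, minimum follow-up 12 months, attrition 10% per year, 1:1 allocation.

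- Hazards, if exponential: control −ln(0.72)/0.5 = 0.657 per year; treatment 0.70 × 0.657 = 0.460 per year.
- Required events (Schoenfeld): 4 × (1.960 + 0.842)² / (ln 0.70)² = 4 × 7.849 / 0.1272 = 247. Freedman's formula gives 253.
- Subjects: with uniform accrual and an attrition hazard of 0.10, the event probability is 0.685 in control and 0.569 in treatment, mean 0.627. Then 247 / 0.627 = 394, within 3% of the plan's 388.
- The stated 265 events do not reproduce as a requirement. They match the number expected from 388 subjects with no attrition (388 × 0.685 = 265.8); with attrition about 243 are expected. That is a separate matter. Because of it, power is shown below at both 247 and 265 events.

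**2. Planned transplants as first events (if the endpoint definition governs).** Assumptions not in the documents: 10% of subjects listed at baseline, transplant rate r = 0.2 to 0.4 per year in listed subjects, 1.5 years of follow-up.

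Listed subjects: 388 × 0.10 = 38.8. With λ the hazard of other primary events, the probability that transplant comes first is r/(r + λ) × [1 − exp(−1.5(r + λ))].

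| r | Control (λ = 0.657) | Treatment (λ = 0.460) | Mean | × 38.8 | Share of 247 | Share of 265 |
|---|---|---|---|---|---|---|
| 0.2 | 0.169 | 0.190 | 0.180 | 7.0 | 2.8% | 2.6% |
| 0.4 | 0.301 | 0.337 | 0.319 | 12.4 | 5.0% | 4.7% |

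So there would be about 7 to 12 such events, roughly 3 to 5% of first events.

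**3. Effect on the hazard ratio and power.** If a share f of control events has HR 1 and the rest has HR 0.70, the mixed HR is approximately 0.70(1 − f) + f. Power = Φ(|ln HR| × √d / 2 − 1.96), with d events.

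| f | HR | Power, d = 265 | Power, d = 247 |
|---|---|---|---|
| 0 | 0.700 | 83% | 80% |
| 3% | 0.709 | 80% | 77% |
| 5% | 0.715 | 78% | 75% |

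Example at f = 5%, d = 265: 0.3355 × 16.28 / 2 − 1.96 = 0.77, and Φ(0.77) = 0.78.

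**4. If the Data Collection Overview governs.** The figures in step 3 do not apply, because a transplant is then not a failure. The primary analysis counts recurrent events, so a transplant ends observation even after an earlier heart failure event. Ignoring competing events, the number of listed subjects cut off this way is at most 38.8 × [1 − exp(−1.5r)] = 10 (r = 0.2) to 18 (r = 0.4). The documents give nothing from which the size or direction of any resulting bias could be computed.

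**The case against.** The strongest reply is that the protocol text is not the whole plan. Medical History is collected, and its fields would sit in the case report forms (Appendix L). Analysis details are deferred to the separate SAP. The Subject Eligibility Committee's items are expressly not exhaustive. The Clinical Events Committee is to write a charter covering minimum data and a classification algorithm. The DSMB asked only that patients be asked, which a single form field would satisfy. This stands in part. A reader might infer that planned transplants cannot be told apart from worsening heart failure in this trial, and the documents do not support that. They support only that the protocol itself specifies neither collecting nor using list status. Adjudication does not clearly fill the gap, since the protocol's definition of worsening heart failure covers visits and hospitalizations and gives no rule for a transplant.

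Second, a reader might infer that sites will treat listed patients differently under the Stage D exclusion and so bias the comparison. Central eligibility review of every subject and stratification by center largely answer this. Listing is balanced between arms in expectation. Bias would need transplant decisions to differ by known arm, which is possible without masking but not shown. Recording list status would not prevent it.

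Third, a reader might infer a larger loss of power by counting every transplant in a listed subject, 10 to 18 in all, as a first event. Many of these subjects would have another primary event first, which is why the range is 7 to 12. The protocol also notes that the recurrent-event analysis may have more than 80% power. The time-to-first-event figures above do not credit that.

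Fourth, a competing-outcomes summary including transplant is already planned by arm. It is useful but is not split by list status.

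**Conclusion.** The point holds as a gap in specification, together with a contradiction. Transplant is a primary component. The feasibility DSMB asked for list status to be obtained for a reason that bears directly on that component, and the protocol names it nowhere in eligibility, baseline data, committee review or covariates. Separately, the Data Collection Overview conflicts with the Primary Efficacy Objective and the endpoint definition on whether a transplant is an event or a censoring time.

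The size is modest. If transplants are events, and under assumed rates of 10% listed, 0.2 to 0.4 transplants per year and 1.5 years of follow-up, HR 0.70 moves to about 0.709 to 0.715. Power then falls from 83% to about 78 to 80% at 265 events, or from 80% to about 75 to 77% at 247. This treats planned transplants as wholly unaffected by the device and uses the arm-averaged share of events as f. If transplants are censored, the issue is possibly informative censoring of unknown size. The finding would narrow if the case report forms or the SAP already capture and use list status. The contradiction within the protocol would still need resolving.

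**What to change.** 1. Reconcile the Primary Efficacy Objective, the Data Collection Overview and the Primary Efficacy Endpoint definition into one rule for transplant in the primary analysis.
2. Add list status (listed or not, and date) as a required pre-randomization item in Table 2 and in the material sent to the Subject Eligibility Committee.
3. Add list status to the baseline covariates under Impact of Covariates on the Potential Treatment Differences.
4. Report transplants in each arm by baseline list status.
5. Prespecify one sensitivity analysis of the primary endpoint in which a transplant in a subject listed at randomization, without a prior adjudicated worsening heart failure event, is a competing event and not a failure.

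How listing relates to the Stage D exclusion is for the sponsor to reconcile.

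The cost is one eCRF field, one covariate, one split in a planned table and one extra analysis. Apart from the reconciliation in item 1, which is needed in any case, the primary test does not change.
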